5.1.4 Post-Treatment Follow-Up Period (Substudy 3)

In Substudy 3, the Post-treatment (PT) Period, subjects will be followed for 48 weeks after the last dose of study drugs for evaluation of the emergence, evolution and persistence of viral resistance to ABT-450/r and ABT-267 and for viral response.

[figure not shown]
All subjects who receive at least 1 dose of DAA will be monitored for viral resistance on an outpatient basis for an additional 48 weeks following the last dose of study drugs, regardless of whether they prematurely discontinue study drug treatment or complete treatment as planned in Substudies 1 and 2. Refer to [Figure 3](#), Subject Flow Chart.

Subjects will return to the study site as outlined in [Table 7](#) (and [Table 8](#) for cirrhotic subjects) for post-treatment visit procedures including resistance monitoring, HCV RNA testing, and assessment of adverse events (for 30 days post-treatment only) and serious adverse events. Substudy 3 will begin the day after the last dose of study drug treatment. Subjects who prematurely discontinue Substudy 3 should return to the site for a PT Week 48/PT Discontinuation Visit as outlined in [Table 7](#) (and [Table 8](#) for cirrhotic subjects).

Some of the Post-Treatment Period study visits and visit activities (including but not limited to vital signs, clinical laboratory tests and concomitant medication assessment) may be conducted in the home or non-hospital/clinic environment at the request of the Investigator and with the agreement of the subject.

All subjects who receive at least one dose of DAA may be offered participation in a separate AbbVie-sponsored observational study to evaluate the durability of virologic response for subjects who achieve SVR or to study the emergence and persistence of resistant variants in subjects who fail treatment.

Figure 3. Subject Flow Chart

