8.1.5 Resistance Analyses

The genes of interest for population sequencing in this study are those encoding full length NS3/4A and NS5A, while for clonal sequencing they are those encoding NS3 amino acids 1 to 181 and NS5A amino acids 1 to 215. For each DAA target, resistance-associated signature amino acid variants will be identified by AbbVie Clinical Virology. Amino acid positions where resistance-associated variants have been identified in vitro and/or in vivo are: 155, 156, and 168 in NS3 for ABT-450; 28, 30, 31, 58, and

93 in NS5A for ABT-267. This list may be expanded if treatment-emerged resistance-conferring variants are identified at additional amino acid positions in DAA-treated patients. The prototypic reference sequences used for analysis will be H77 for genotype 1a or Con1 for genotype 1b.

Only samples with an HCV RNA level of ≥ 1000 IU/mL will undergo sequence analysis in order to allow accurate assessment of products of amplification. Therefore, if the HCV RNA level at the time of virologic failure is < 1000 IU/mL, the sample closest in time after the failure with an HCV RNA level ≥ 1000 IU/mL will be used. Clonal sequencing of a given target will be performed only if no variants are detected at signature resistance-associated amino acid positions by population sequencing in that sample. In addition, clonal sequencing may be performed if there is a complex mixture of amino acids at one or more signature resistance-associated position that cannot be resolved by population sequencing.

Included time points for analyses on samples from subjects who experience virologic failure (as defined in Section 5.4.1.1) are (1) time of virologic failure or sample closest in time after failure with an HCV RNA level of ≥ 1000 IU/mL, (2) 24 weeks post-DAA treatment, provided that resistance-associated variants were detected by either population or clonal sequencing at the time of failure, and (3) 48 weeks post-DAA treatment, provided that resistance-associated variants were detected by either population or clonal sequencing at post-DAA treatment Week 24.

The following definitions will be used in the resistance analyses:

- Baseline variant: a variant (by population sequencing) in a baseline sample determined by comparison of the amino acid sequence of the baseline sample to the appropriate prototypic reference amino acid sequence for a given DAA target (NS3 or NS5A).

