## 4.2 Design Diagram

This is a multicenter, Phase 2, open-label, single-arm, combination treatment study evaluating ABT-450/r in combination with ABT-267, pegIFN and RBV for 24 weeks followed by pegIFN and RBV alone for an additional 24 weeks in HCV genotype 1-infected subjects who have experienced virologic failure while participating in a previous pegIFN-free Abbott/AbbVie DAA combination study. This study consists of a pre-screening period, a screening period and three substudies:

- Substudy 1 (Treatment Intensification [TI]): 24 weeks of therapy with ABT-450/r plus ABT-267 plus pegIFN plus RBV;
- Substudy 2 (pegIFN/RBV [PR] Treatment): 24 weeks of pegIFN and RBV therapy alone;
- Substudy 3 (Post-treatment [PT] Follow-up Period): 48 weeks after last dose of any study drug for resistance monitoring and HCV RNA viral load testing.

A study schematic is shown below (Figure 1).

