**Figure 1. Study M13-101 Schematic**

There is one treatment group for this study. During Substudy 1 (TI Period), subjects will receive ABT-450/r 200/100 mg daily (QD), ABT-267 25 mg QD, pegIFN 180 µg once weekly, and weight-based RBV twice daily. During Substudy 2 (PR Treatment

Period), subjects will receive 24 weeks of pegIFN/RBV. All subjects who receive at least one dose study drug will be followed for 48 weeks in the Post-Treatment period. The duration of the study will be 96 weeks, not including a screening period.

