**Table 2. PR Treatment (Substudy 2)/Post-DAA Visit Windows**

Scheduled Time	Nominal Study (DAA Study Drug End Day)	Time Window (DAA Study Drug End Days Range)
PR/Post-DAA Week 2	14	3 to 21
PR/Post-DAA Week 4	28	22 to 42
PR/Post-DAA Week 8	56	43 to 70
PR/Post-DAA Week 12	84	71 to 126
PR/Post-DAA Week 24	168	127 to 210
PR/Post-DAA Week 36 a	252	211 to 294
PR/Post-DAA Week 48 a	336	295 to 378
Final Treatment Visitb	Last Visit with Study Day > 1 and Study Drug End Day ≤ 2	

a. These Substudy 2 visits are only needed for subjects who did not complete 24 weeks for pegIFN/RBV in Substudy 1 such that a subject completes a total of 48 weeks of pegIFN/RBV across Substudies 1 and 2. However, the Post-DAA Week 48 window may be used for resistance analyses, regardless of the number of Substudy 2 visits.

b. Final Treatment Visit is defined for all subjects, regardless of whether the subject enters Substudy 2.

Note: For efficacy analyses of HCV RNA and safety analyses, all scheduled time points, except Final Treatment Visit, will apply only to subjects who received pegIFN/RBV in Substudy 2.

For efficacy analyses of HCV RNA and safety analyses, data must also have DAA Study Drug End Day > 2 and PR End Day ≤ 2 for all scheduled time points, except Final Treatment Visit.

For resistance analyses, data must have DAA Study Drug End Day > 2 for all scheduled time points.

Resistance data included in Post-DAA windows may have been collected either during PR Treatment or Post-Treatment.

The result closest to the scheduled timepoint will be used.

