## 10.6 Resistance Analyses

The genes of interest for population sequencing in this study are those encoding full length NS3/4A and NS5A, while for clonal sequencing they are those encoding NS3 amino acids 1 to 181 and NS5A amino acids 1 to 215. For each DAA target, signature amino acid positions are 1) for paritaprevir: 36, 43, 55, 56, 80, 155, 156, and 168 in NS3 for genotype 1a; 55, 56, 155, 156, and 168 in NS3 for genotype 1b; and 2) for ombitasvir: 24, 28, 29, 30, 31, 32, 58, 62, 92, and 93 in NS5A for genotype 1a; 24, 28, 29, 30, 31, 32, 58, 62, 92, and 93 in NS5A for genotype 1b. The prototypic reference sequences used for analysis will be H77 for genotype 1a or Con1 for genotype 1b. Only samples with an HCV RNA level of  $\geq$  1000 IU/mL will undergo sequence analysis in order to allow accurate assessment of products of amplification. Therefore, if the HCV RNA level at the time of virologic failure is < 1000 IU/mL, the sample closest in time after the failure with an HCV RNA level  $\geq$  1000 IU/mL will be used. Clonal sequencing of a given target will be performed only if no variants are detected at signature amino acid positions by population sequencing in that sample. In addition, clonal sequencing may be performed if there is a complex mixture of amino acids at one or more signature position that cannot be resolved by population sequencing.

Included time points for analyses on samples from subjects who experience virologic failure (as defined in Section 5.4.1.1) are (1) time of virologic failure or sample closest in time after failure with an HCV RNA level of  $\geq 1000$  IU/mL, (2) 24 weeks post-DAA treatment, provided that variants at signature amino acid positions were detected by either population or clonal sequencing at the time of failure, and (3) 48 weeks post-DAA treatment, provided that variants at signature amino acid positions were detected by either population or clonal sequencing at post-DAA treatment Week 24.

The following definitions will be used in the resistance analyses:

- Baseline variant: a variant (by population sequencing) in a baseline sample determined by comparison of the amino acid sequence of the baseline sample to the appropriate prototypic reference amino acid sequence for a given DAA target (NS3 or NS5A).
- Post-baseline variant by population sequencing: an amino acid variant in a post-baseline time point sample that was not detected at baseline and is detectable by population sequencing.

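### Full-course completers whose relapse is first detected after PT Week 4 get no resistance sequencing beyond the failure sample, because the follow-up condition rests on a window that closes before the relapse

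*SAP*

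**What the plan says.** SAP 10.6 names three time points for subjects with virologic failure, which under protocol 5.4.1.1 includes relapse. The first is the failure sample, or the nearest later one that can be sequenced. The second is 24 weeks post-DAA, if variants at signature positions were found at failure. The third is 48 weeks post-DAA, but only "provided that variants at signature amino acid positions were detected by either population or clonal sequencing at post-DAA treatment Week 24". Protocol 8.1.5 has the same chain, ending "provided that resistance-associated variants were detected by either population or clonal sequencing at post-DAA treatment Week 24". Both require HCV RNA of at least 1000 IU/mL for sequencing.

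SAP 6.2 assigns resistance data with Tables 1 and 2, on a clock that starts at the last DAA dose and disregards when pegIFN/RBV ends. Table 2 adds that "the Post-DAA Week 48 window may be used for resistance analyses, regardless of the number of Substudy 2 visits", and that post-DAA windows may hold samples taken during pegIFN/RBV or after it. Table 3, the post-treatment table, is not named for resistance.

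Protocol 5.1.4 gives the purpose of Substudy 3: "subjects will be followed for 48 weeks after the last dose of study drugs for evaluation of the emergence, evolution and persistence of viral resistance". Protocol Table 7 schedules a resistance sample at all seven visits: PT Weeks 2, 4, 8, 12, 24, 36 and 48.

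**The concern.** Relapse is counted from the end of all study drug, while resistance follow-up is counted from the end of the DAAs. In a subject who takes the whole course, the two clocks differ by about 24 weeks. The follow-up condition is then judged on a window centred on the end of treatment, when a future relapser is suppressed and has nothing to sequence.

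At stake is whether variants seen at relapse persist or revert. Protocol 3.2 treats that as relevant to risk, since variants that persist off treatment may limit later options. The SAP anticipates later relapses: SAP 10.1 defines relapse up to the SVR12 assessment, within the SVR24 window and after it.

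**Working it through.** **Inputs**
- SAP 4.2: Substudy 1 is "24 weeks of therapy with ABT-450/r plus ABT-267 plus pegIFN plus RBV", Substudy 2 is "24 weeks of pegIFN and RBV therapy alone", and Substudy 3 runs "48 weeks after last dose of any study drug for resistance monitoring and HCV RNA viral load testing".
- SAP 6.1: the DAA clock has day 0 at the last DAA dose; the study-drug clock has day 0 at the last pegIFN injection plus 7 days.
- SAP Table 2: post-DAA Week 24 is days 127–210, Week 36 is 211–294, Week 48 is 295–378 (the last window).
- SAP Table 3: nominal PT days are 14, 28, 56, 84, 168, 252 and 336.
- SAP 10.1: LLOQ is 25 IU/mL; completion means DAA ≥ 161 days and pegIFN/RBV ≥ 252 days.

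**Step 1. Reproduce the stated duration.** 24 + 24 + 48 = 96 weeks. This matches the SAP: "The duration of the study will be 96 weeks, not including a screening period".

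**Step 2. Distance between the clocks.** Nominally 24 × 7 = 168 days. With 48 weekly injections from Day 1, the last falls on Day 1 + 7 × 47 = 330; adding 7 gives Day 337, and 337 − 168 = 169. The offset for a full course is therefore 168–169 days.

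**Step 3. Place the PT visits on the DAA clock.** Post-DAA day = nominal PT day + offset.

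| Visit | Post-DAA day (168 / 169) | Resistance window |
|---|---|---|
| PT Week 2 | 182 / 183 | Week 24 |
| PT Week 4 | 196 / 197 | Week 24 |
| PT Week 8 | 224 / 225 | Week 36 |
| PT Week 12 | 252 / 253 | Week 36 |
| PT Week 24 | 336 / 337 | Week 48 |
| PT Week 36 | 420 / 421 | none |
| PT Week 48 | 504 / 505 | none |

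The Week 24 window closes at Study Drug End Day 210 − 168 = 42 (or 210 − 169 = 41). Week 36 is not a sequencing time point in SAP 10.6.

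**Step 4. Apply the rule to a full-course completer with variants at failure.**
- Relapse first seen at PT Week 2 or 4: a sequenceable sample can lie in the Week 24 window. The condition can be met, and PT Week 24 gives a sample 22 or 20 weeks later.
- Relapse first seen at PT Week 8 or 12: every sample in the Week 24 window predates it and is expected to be below 25 IU/mL, against the 1000 needed. The condition fails, and the PT Week 24 sample is not used although day 336 is exactly nominal post-DAA Week 48.
- Relapse first seen at PT Week 24: the failure sample is itself the day 336 sample, and later visits have no window.
- Relapse first seen at PT Week 36: PT Week 48 remains, with no window.
- Relapse first seen at PT Week 48: no later visit exists.

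**Step 5. Shorter courses.** PT Week 8 enters the Week 24 window if the offset is at most 210 − 56 = 154 days, and PT Week 12 if it is at most 210 − 84 = 126. At the completer minimum, the offset is 252 − 168 = 84 (or 252 − 161 = 91). PT Weeks 8 and 12 then fall on days 140 and 168 (147 and 175), and PT Week 36 on day 336 (343). Relapses seen up to PT Week 12 are covered; one first seen at PT Week 24 (day 252 or 259) is not. If all drugs stop together, the offset is about 0, post-DAA Weeks 24 and 48 coincide with PT Weeks 24 and 48, and the rule works.

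**Step 6. Share affected.** Among full-course relapsers it is 1 minus the share first detected by PT Week 4. The documents give no such share. On assumed values of 20%, 50% and 80%, the affected share is 80%, 50% and 20%.

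**Step 7. Samples available if timed from failure.** From PT Weeks 24, 36 and 48: relapse at PT Week 8 has later samples at 16, 28 and 40 weeks; at PT Week 12, at 12, 24 and 36 weeks; at PT Week 24, at 12 and 24 weeks.

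**The case against.** The strongest reply is that the clock is deliberate. SAP 6.2 says resistance windows disregard pegIFN/RBV, and protocol 3.0 describes reversion as something that happens once drug pressure is removed, so time since the last DAA dose is meaningful. On that clock the failure sample already carries information: at PT Week 12 it is 252 / 7 = 36 weeks off DAAs, and at PT Week 24 it is at the nominal post-DAA Week 48 point. This stands, and is a reason to keep reporting time since DAA. But one sample shows only that variants are present; it cannot show whether they persist or revert afterwards.

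The consequence is also limited. Persistence is neither a primary nor a secondary objective, the output is mainly by-subject listings, enrolment is up to 35, and no SVR estimate changes. Protocol 5.2.3.3 leaves treatment after relapse to the investigator, so some later samples may follow new therapy. All of this stands and bears on priority. The separate observational study in protocol 5.1.4 is optional and does not fill the gap in this analysis.

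A reader might infer that persistence is lost in most relapsers. The documents do not support that: they give no distribution of relapse timing. Nor does the Week 24 sample always precede relapse, since PT Weeks 2 and 4 lie inside the window.

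**Conclusion.** The point holds for a defined group: subjects who take about 24 weeks of pegIFN/RBV after the DAAs and whose relapse is first detected after PT Week 4, that is, after about Study Drug End Day 42. For them the rule yields the failure sample and nothing later, although resistance samples are collected throughout Substudy 3 and persistence is one of its purposes. It rests on nominal visit timing and on HCV RNA staying below 1000 IU/mL until relapse is detected.

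It should not be read as a failure of the rule for every subject. Shorter pegIFN/RBV courses bring later visits into the windows, and stopping all drugs together removes the problem. The loss of the PT Week 36 and 48 samples likewise depends on the offset: PT Week 36 is inside a window if the offset is at most 378 − 252 = 126 days, and PT Week 48 if at most 378 − 336 = 42. A relapse first seen at PT Week 48 has no later sample under any rule.

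One ambiguity could widen the gap. Table 2 takes the result closest to the scheduled time. If that means the closest collected sample, rather than the closest that can be sequenced, the end-of-treatment sample is chosen and full-course relapsers seen at PT Week 2 or 4 are blocked as well. The SAP does not settle this.

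**What to change.** Amend SAP 10.6, protocol 8.1.5 and SAP Table 2 as follows.

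- For failures first detected after the end of DAA dosing, require only that variants were detected at failure or in the most recent sequenced sample.
- In those subjects, sequence the scheduled sample closest to 24 weeks after failure and the last available one up to PT Week 48, where they exist, have HCV RNA of at least 1000 IU/mL and precede any new HCV therapy. For a relapse at PT Week 24 these are the same sample.
- Report time since the last DAA dose alongside time since failure.
- If results are still tabulated by post-DAA window, add windows for days 379–462 and 463–546. They follow directly on day 378, keep the present 84-day width (378 − 295 + 1 = 84) and contain days 420 and 504.
- State that the closest sequenceable sample in a window is used, so that an end-of-treatment sample below LLOQ does not block relapses seen at PT Week 2 or 4.
- Keep the present rule for failures during DAA dosing.

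The cost is a wording change and the sequencing of a few more stored samples. No visit or blood draw is added.

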already have selected resistance to one or more DAA class in the setting of their prior treatment failure. Therefore, the risk of incurring a greater degree of viral drug resistance (and the resulting loss of additional treatment options) must be weighed against the possible benefit of an efficacious treatment regimen. Since this balance may be different depending on multiple factors (including prior treatment experience, stage of liver disease, other available treatment options, IL28B host genotype and others), this study will be made available on a purely optional basis to all subjects who previously experienced virologic failure in an AbbVie/Abbott DAA combination trial. It is expected that subjects will make a decision regarding participation in consultation with the investigator. However, since prior non-responders (null or partial response) to pegIFN/RBV may have a suboptimal response to a second course of pegIFN and RBV, this population will only be eligible if population sequencing of HCV NS3/4A protease and NS5A from a sample collected at the Pre-screening Visit does not detect variants at positions known to be associated with reduced susceptibility to ABT-450 and ABT-267. Likewise, even subjects who had an initial response to pegIFN/RBV plus telaprevir or boceprevir and then failed (due to relapse or breakthrough) may, in fact, be poor responders to interferon, and the initial virologic response may have reflected suppression due to the protease inhibitor. Hence, subjects who received pegIFN/RBV plus telaprevir in the previous AbbVie/Abbott study will only be eligible if population sequencing does not detect ABT-450 or ABT-267 resistance-associated variants.

In summary, the risks associated with the individual study drugs to be administered in Study M13-101 have been well characterized and appear limited and manageable. Subjects will be closely monitored for any potential risks which may occur when the DAAs are dosed in combination, including risks of toxicity and of virologic failure. Given the potential benefit of achieving cure in a population of HCV-infected subjects with limited available treatment options, as well as the manageable risks associated with the planned therapy, the risk-benefit comparison is considered favorable.

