- Post-baseline variant by population sequencing: an amino acid variant in a post-baseline time point sample that was not detected at baseline and is detectable by population sequencing.

- Post-baseline variant by clonal sequencing: a variant at a signature resistance-associated amino acid position that was not present by population sequencing at baseline that is detected in a post-baseline sample by clonal sequencing in at least 2 clones from that sample (among the subset of subjects for whom clonal sequencing is performed).
- Emerged variant by population sequencing: a post-baseline variant that is observed in 2 or more subjects of the same HCV subgenotype by population sequencing.
- Linked variant by population sequencing: 2 or more signature resistance-associated or emerged amino acid variants identified within a target by population sequencing, where at least one of the variants is at a signature position, and no mixture of amino acids is detected at either position.
- Linked variant by clonal sequencing: at least 2 clones from a given sample containing the same 2 or more signature resistance-associated amino acid variants by clonal sequencing.

For those subjects whose baseline sample has an HCV RNA level ≥ 1000 IU/mL, a listing by subject of all baseline variants relative to prototypic reference sequence at signature resistance-associated amino acid positions will be provided for each DAA target (NS3 and NS5A).

The following analyses will be performed on the samples from subjects who experienced virologic failure and have post-baseline resistance data available.

The HCV amino acid sequence as determined by population sequencing will be compared with the baseline and appropriate prototypic reference amino acid sequences. Listings by subject of all post-baseline variants detected by population sequencing relative to the baseline amino acid sequences will be provided for each DAA target (NS3 and NS5A). In addition, listings by subject of variants detected by population sequencing at signature resistance-associated amino acid positions relative to baseline and the appropriate prototypic reference amino acid sequences will be provided.

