For the subset of samples for which clonal sequencing is performed, the amino acid variants determined by clonal sequencing will be summarized by counting the number of clones whose amino acid sequence does not match that of the population baseline sequence by subject at each time point and amino acid position, out of the total number of clones analyzed. Listings by subject of post-baseline variants at signature resistance-associated positions detected by clonal sequencing will be provided for each DAA target.

Linkage between emerged or signature variants by population sequencing will also be evaluated. A listing by subject and time point of the linked variants by population sequencing for each target will be provided. Furthermore, where clonal sequencing is performed and the sample has at least 2 clones with the same 2 or more signature resistance-associated amino acid variants within a DAA target, then a listing by subject and time point of the linked variants by clonal sequencing will be provided.

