- Post-baseline variant by clonal sequencing: a variant relative to prototypic reference sequence at a signature amino acid position by clonal sequencing in at least 2 clones from that sample (among the subset of subjects for whom clonal sequencing is performed).
- Emerged variant by population sequencing: a post-baseline variant that is observed in 2 or more subjects of the same HCV subtype by population sequencing.
- Linked variant by population sequencing: 2 or more signature or emerged amino acid variants identified within a target by population sequencing, where at least one of the variants is at a signature position, and no mixture of amino acids is detected at either position.

For those subjects whose baseline sample has an HCV RNA level  $\geq 1000$  IU/mL, a listing by subject of all baseline variants relative to prototypic reference sequence at signature amino acid positions will be provided for each DAA target (NS3 and NS5A).

The following analyses will be performed on the samples from subjects who experienced virologic failure and have post-baseline resistance data available.

The HCV amino acid sequence as determined by population sequencing will be compared with the baseline and appropriate prototypic reference amino acid sequences. Listings by subject of all post-baseline variants detected by population sequencing relative to the baseline amino acid sequences will be provided for each DAA target (NS3 and NS5A). In addition, listings by subject of variants detected by population sequencing at signature amino acid positions relative to baseline and the appropriate prototypic reference amino acid sequences will be provided.

For the subset of samples for which clonal sequencing is performed, the amino acid variants determined by clonal sequencing will be summarized by counting the number of clones whose amino acid sequence does not match that of the prototypic reference sequence by subject at each time point and amino acid position, out of the total number of clones analyzed. Listings by subject of post-baseline variants at signature positions detected by clonal sequencing will be provided for each DAA target.

Linkage between emerged or signature variants by population sequencing will also be evaluated. A listing by subject and time point of the linked variants by population sequencing for each target will be provided.

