## 12.0 Summary of Changes

### 12.1.1 Summary of Changes Between the Latest Version of Protocol and the Version 1 of the SAP

- Remove history of bleeding disorders, tobacco and alcohol use status and treatment during the gap between the prior study and Study M13-101 from demographic and baseline characteristics summary (see Section 7.1).
- Add sensitivity analysis of SVR12 using a Modified Intent-to-Treat Genotype and Virologic Failure (mITT-GT + VF) population (see Section 10.4).
- The list of signature amino acid positions important for the NS3/4A protease and NS5A inhibitor class were updated for resistance analyses (see Section 10.6).
- Change "EOTR" to "Final Treatment Visit Response" to avoid confusion with the definition of "EOTR" in other HCV studies with DAA regimens not including pegIFN and change "rebound" to "breakthrough" to align with terminology in newer HCV studies.
- Remove EVR, SVR12planned, SVR24planned, and Kaplan-Meier curves of the time to suppression and the time to relapse from additional efficacy endpoints to be consistent with analysis plans for newer HCV studies.
- Remove logistic regression to explore potential predictors of response due to the small sample size of the study.
- Replace exact binomial method with Wilson score method for confidence interval calculation.
- Remove summaries of baseline characteristics and efficacy endpoints by treatment in previous study. Add SVR12 subgroup analysis by treatment in previous study.

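### SAP 10.6 judges clonal post-baseline variants against the reference strain only, so some variants carried over from the earlier DAA failure can be listed as post-baseline

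*SAP*

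**What the plan says.** Protocol 8.1.5 (Resistance Analyses) limits the clonal post-baseline variant to one at a signature position "that was not present by population sequencing at baseline that is detected in a post-baseline sample by clonal sequencing" in at least 2 clones. Its clone summary counts clones "whose amino acid sequence does not match that of the population baseline sequence". Protocol 5.3.3.3 (Resistance Variables) covers both sequencing methods and asks for post-baseline variants to be compared with baseline and with the reference.

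SAP 10.6 (Resistance Analyses) defines the same term as "a variant relative to prototypic reference sequence at a signature amino acid position by clonal sequencing in at least 2 clones", with no condition on the subject's baseline. Its clone summary counts clones "whose amino acid sequence does not match that of the prototypic reference sequence". In the same section, the population-sequencing definition still requires that the variant was not detected at baseline.

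For resistance, SAP 12.1.1 declares one change from the protocol: "The list of signature amino acid positions important for the NS3/4A protease and NS5A inhibitor class were updated for resistance analyses". It does not mention the comparator.

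**The concern.** All subjects enter after virologic failure on an earlier DAA combination. Protocol 3.2 assumes that many will "already have selected resistance to one or more DAA class in the setting of their prior treatment failure", and Protocol 5.1.1 lets most enrol whatever variants are found; the exceptions are prior null or partial responders and subjects who failed the telaprevir regimen. Differences from the reference at Day 1 are therefore expected.

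Protocol 5.1.4 sets out to describe the emergence, evolution and persistence of resistance. A post-baseline label that ignores baseline mixes the first with the last: a residual old variant and a newly selected one get the same entry. The label also has two meanings within SAP 10.6, depending on the sequencing method, and a reader of the SAP's change list would not know that the clonal meaning had moved away from the protocol.

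**Working it through.** The documents give no figure to reproduce, so the check is a comparison of rules.

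**1. When clonal sequencing is done.** Under SAP 10.6 a target is cloned only if population sequencing of that sample shows no variant at a signature position. It may also be cloned if a complex mixture at a signature position cannot be resolved.

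**2. Where the two definitions part.** Take one variant at a signature position. Assume that the optional cloning of mixtures is used and that at least 2 clones carry the variant. The last two columns show whether it is listed as post-baseline by clonal sequencing.

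| At baseline (population) | Post-baseline (population) | Unresolved mixture | Cloned | Protocol | SAP |
|---|---|---|---|---|---|
| no | no | no | yes | yes | yes |
| no | no | yes | yes | yes | yes |
| no | yes | no | no | – | – |
| no | yes | yes | yes | yes | yes |
| yes | no | no | yes | **no** | **yes** |
| yes | no | yes | yes | **no** | **yes** |
| yes | yes | no | no | – | – |
| yes | yes | yes | yes | **no** | **yes** |

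The rules differ in 3 of 8 cases. All three need a variant already seen at baseline that has since dropped below population detection or lies in an unresolved mixture. With the protocol condition restored, the count is 0 of 8. These are logical cases, not frequencies.

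**3. Example.** A variant at NS3 168 is present at Day 1 by population sequencing. In a later sample the population sequence shows no signature variant in NS3, so NS3 is cloned, and 2 clones still carry the variant. The SAP lists it as post-baseline; the protocol does not. The situation is plausible: Protocol 3.0 discusses resistant populations returning to mainly wild type off drug, and SAP 10.6 allows sequencing at 24 and 48 weeks post-DAA.

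**4. Can a minority variant reach 2 clones?** Neither document gives a clone number or a variant frequency, so both are assumed. With n clones and frequency f, P(at least 2) = 1 − (1 − f)^n − n·f·(1 − f)^(n − 1). For n = 20 and f = 5%: 1 − 0.3585 − 0.3774 = 0.264.

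| f | n = 20 | n = 40 | n = 80 |
|---|---|---|---|
| 1% | 0.017 | 0.061 | 0.191 |
| 5% | 0.264 | 0.601 | 0.914 |
| 10% | 0.608 | 0.920 | 0.998 |
| 15% | 0.824 | 0.988 | 1.000 |

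The 2-clone rule screens out very rare residual variants. It does not screen out those at 5–10% once a moderate number of clones is read.

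**5. Clone counts.** The SAP summarises clones by amino acid position and states no restriction to signature positions; the cloned regions are NS3 1–181 and NS5A 1–215. A fixed difference between the subject's virus and H77 or Con1 is therefore counted as a mismatch in every clone. A fixed difference at a signature position would normally be seen by population sequencing and stop cloning, so this arises mainly at non-signature positions. Conversely, a clone that has reverted from a baseline variant to the reference counts as no mismatch under the SAP, but as a mismatch under the protocol.

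**The case against.** A reader might infer that resistance carried over from the earlier trial will be reported as arising in this one, or that the whole resistance analysis overstates emergence and hides reversion. The documents do not support that. The SAP's only emergence term, the emerged variant, rests on population sequencing and on a definition that still excludes variants detected at baseline. A carried-over variant that still dominates is seen by population sequencing, so its target is not normally cloned. Reversion at population level is covered by the listings that compare each sample with both baseline and reference. The SAP also lists baseline signature variants by subject where baseline HCV RNA is at least 1000 IU/mL, so carry-over can be traced by hand in a study planned for up to 35 subjects.

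Nor does the longer list of signature positions show that the problem has grown. NS3 goes from 3 positions to 8 (genotype 1a) or 5 (1b), and NS5A from 5 to 10. More positions let more pre-existing differences qualify, but they also produce more population hits and hence fewer cloned samples. The net direction is unknown.

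The reference comparator also has a real merit. In the NS3 168 example it keeps the two residual resistant clones in view, whereas the protocol rule alone drops them from the post-baseline listing and counts the wild-type clones as the mismatches. Since persistence is one of the aims, that information should be kept.

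All of this narrows the consequence. It does not explain why one label has two meanings, why the baseline comparison required by Protocol 5.3.3.3 is missing from the clonal analysis, or why the change is not declared.

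**Conclusion.** The point stands in a limited form. SAP 10.6 departs from Protocol 8.1.5 and 5.3.3.3 on both clonal comparators, is inconsistent with its own population-sequencing definition, and does not say so in 12.1.1. The effect is confined to the clonal post-baseline listing and the clone counts. Mislabelling needs three things together: a variant detected at baseline, its fall below population detection or its presence in an unresolved mixture, and at least 2 clones carrying it. How often that happens cannot be derived, because the documents give no failure count, carry-over rate, clone number or variant frequency; the probabilities in the working are illustrations only. SVR12, SVR24, eRVR, the population listings and the emerged-variant definition are untouched. It should be corrected because the label would be wrong in just the cases where persistence and new selection need to be told apart.

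One limitation remains in either version: a variant present at baseline only below population detection would still be called post-baseline, because neither definition uses baseline clones.

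**What to change.** In SAP 10.6:

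- Restore, for the clonal post-baseline variant, the condition that it was not present by population sequencing at the subject's baseline; keep the 2-clone rule.
- Report clone counts against the subject's population baseline sequence.
- Keep the H77/Con1 comparison as a separate listing, titled as variants relative to reference, with a yes/no flag for presence at baseline, so that residual resistant clones stay visible.

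In SAP 12.1.1, declare any departure from Protocol 8.1.5 that remains.

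The cost is SAP wording, a second comparator in the clonal programs and one extra listing column. No new samples, sequencing or data are needed, and no efficacy result changes.
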